We will retain Study Screening Visit data from ineligible subjects; these data will be analyzed anonymously in order to obtain descriptive and comparative findings of deaf community members who did not qualify for the study. Ineligible subjects will be asked to join the NCDHR contact list to be notified of future studies (see RSRB approved protocol #33598 Deaf Health Research Contact List). Joining the Contact List is an entirely separate activity from their involvement in the DWW Study Screening Visit; the Contact List has its own stand-alone protocol for how to sign up on the NCDHR website. Other studies conducted by NCDHR have included information about joining the Contact List at the end of study participation. Information that ineligible DWW subjects may provide as part of the Contact List is completely separate from DWW and will never be linked to DWW study data.

Medical Clearance Process

As part of the baseline study screening interview, subjects will be asked a brief series of questions that will determine their eligibility to participate in the study (see: Physical Activity Readiness Questionnaire). To determine any potential health related concerns, there are questions that ask the following:

- 2 questions about heart attack or stroke in the past 6 months;
- 5 questions ask about chest pain, heart condition, dizziness, shortness of breath, and other limitations during physical activity;
- 2 questions about recent overnight hospitalization and emergency room visits;
- 1 question to determine whether the subject has had weight loss surgery in the previous two years;
- 1 question to determine if the subject is pregnant.
- Calculate BMI using self-reported height and weight.

If a subject answers positively to any of these items, or has a BMI of 45.0 or higher, they will be required to obtain permission from their Primary Care Provider (or maternity care clinician as appropriate) to participate in the DWW Intervention as it is designed (see Physician Permission Letters / Tracking Form uploaded in the online application). First, subjects who fall under this criteria will be asked to sign a HIPAA Authorization form - SH 48 MR (Authorization for Release of Medical / Behavioral Health information; this fillable PDF form is found here:

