<https://www.urmc.rochester.edu/health-information-management/roi-forms.aspx> . Once the subject completes this form, this will allow our study team to prepare the medical clearance letter that the subject will then give to their healthcare provider (the letter will state that the subject reports having a heart attack or stroke or weight loss surgery or pregnancy or BMI over 45.0). There are two levels of permission: one to obtain clearance to participate in the whole DWW intervention, and the other to participate only in the educational and dietary components (but be excluded from the physical activity components). Subjects will be required to obtain permission from their provider on their own (using the Physician Permission Form) and to return the completed form to the research team in order to participate in the relevant 16-week intervention component(s). These procedures were successfully implemented in the first two

clinical trials of Deaf Weight Wise; in fact, only a very small proportion of participants in the first two clinical trials needed permission from their provider based on their screening answers, and were able to successfully get that permission.

At the time of enrollment/baseline appointment, we will still enroll the subject even if medical clearance is required for the DWW intervention component. If the subject does not obtain medical clearance before their 16-week zoom-based intervention begins, the research team will consult with the PI ([name] is also a physician) to determine whether participation should be halted entirely or whether the subject should be encouraged to not engage in the exercise or diet modification components. There are no other language-accessible health intervention programs for Deaf sign language users available. If we decline enrollment entirely based on needing provider permission for only those with a health issue, this team feels it is a missed opportunity for these Deaf participant(s), given the minimal risk nature of the study and the benefit to promoting healthy lifestyle. However, if we allow enrollment at the point of screening, and then await provider permission before the intervention starts, we help to ensure that these Deaf participants will not have missed an opportunity to participate. Based on the timing of each site's enrollment, there may not otherwise be an opportunity for these particular Deaf participant(s) in the future if we decline enrollment at that point of screening.

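### The protocol's description of the medical clearance letter omits the symptom and heart-condition category that itself triggers clearance

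*Combined protocol and SAP*

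**What the plan says.** Clearance is described in two places.

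The Inclusion Criteria (Section II, item 5) give five reasons for needing a provider's permission: a recent cardiovascular event; a heart condition, symptoms or another reason not to exercise; recent weight loss surgery; pregnancy; and a BMI over 45.

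Medical Clearance Process (Section III) lists the screening questions. Besides those on heart attack or stroke, surgery and pregnancy, they include "5 questions ask about chest pain, heart condition, dizziness, shortness of breath, and other limitations during physical activity" and "2 questions about recent overnight hospitalization and emergency room visits". The rule is: "If a subject answers positively to any of these items, or has a BMI of 45.0 or higher, they will be required to obtain permission". The section refers to templates held elsewhere ("see Physician Permission Letters / Tracking Form uploaded in the online application").

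On the letter's content, it says that "the letter will state that the subject reports having a heart attack or stroke or weight loss surgery or pregnancy or BMI over 45.0". On the decision asked of the provider, it says: "There are two levels of permission: one to obtain clearance to participate in the whole DWW intervention"; the other level covers education and diet without physical activity. Subjects get the permission themselves and must return the completed form before joining the relevant components. If clearance has not arrived by the start of the program, the team consults the physician-investigator to "determine whether participation should be halted entirely or whether the subject should be encouraged to not engage in the exercise or diet modification components".

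**The concern.** The letter tells the provider why permission is being sought. If it is written as the protocol describes it, a subject whose only trigger was chest pain or dizziness would carry a letter that does not mention it. The provider would then choose between full participation and participation without exercise, and the reason for the referral bears directly on that choice. The program aims for more than 150 minutes of physical activity a week (Section III, Overall study design), so the choice matters.

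A related weakness is what happens when no form comes back. The section first makes the returned form a condition of taking part in the relevant components. It then allows an uncleared subject simply to be encouraged to leave out exercise or diet change. The second statement undercuts the first.

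**Working it through.** The protocol gives no figure to reproduce. The check is a count of the items that trigger clearance against those named in the letter sentence. The triggers come from Medical Clearance Process and the categories from the Inclusion Criteria, numbered as there.

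| Trigger | Items | Inclusion Criteria category | Named in letter sentence |
|---|---|---|---|
| Heart attack, stroke | 2 | 1 | Yes |
| Symptoms, heart condition, limits on activity | 5 | 2 (shortness of breath not named there) | No |
| Overnight hospital stay, emergency visit | 2 | None | No |
| Weight loss surgery | 1 | 3 | Yes |
| Pregnancy | 1 | 4 | Yes |
| BMI | 1 | 5 | Yes |

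Count by item:
- Triggers: 2 + 5 + 2 + 1 + 1 = 11 questions, plus BMI = 12.
- Named: 2 + 1 + 1 + 1 = 5.
- Not named: 5 + 2 = 7. Check: 5 + 7 = 12.

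Count by category: categories 1, 3, 4 and 5 are named and category 2 is not, so 4 of 5 are covered.

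The protocol does not state the total of 12. It is the sum of the listed questions, with BMI as one item and both cardiovascular-event questions treated as covered. The two counts differ because one unnamed category holds most of the unnamed questions, and because hospital and emergency visits are triggers only in Medical Clearance Process. The omission of category 2 does not depend on which count is used. The BMI threshold is 45.0 or higher in the trigger rule and over 45 elsewhere, which changes neither count.

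Who a change can reach:
- Section V.1 set an enrollment deadline of January 18, 2023.
- The July 13, 2023 modification adds one last group of up to 10 subjects, starting in mid-August 2023.
- A change made now can therefore reach at most 10 subjects.

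The protocol gives no rate of needing clearance. It says only that very few subjects in the two earlier trials did. It does not say which triggers they had. The number of letters that would lack their trigger cannot be estimated from this.

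**The case against.** The strongest objection is that the templates, not a parenthesis in the protocol, decide what a provider is told. The letters were uploaded separately, and the provider also completes a Physician Permission Form whose content the protocol does not describe. Either may name the trigger. Read literally, the sentence would leave a subject with chest pain alone holding a letter in which no listed reason applies, so it may be shorthand for staff entering the actual reason. This stands, and it limits the finding to the description. It does not remove the mismatch: the sentence says what the letter will state and does not present its list as examples.

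Other safeguards exist. Permission comes from the subject's own primary care or maternity clinician, who may know the history, and the subject can explain the reason. Baseline data are reviewed for ineligibility, the readiness questionnaire is repeated at follow-up, and adverse-event reporting covers renewed review of clearance. The procedures were also used in both earlier trials, where the few subjects who needed permission obtained it. These points reduce the risk. None of them shows that the provider is told the trigger when deciding.

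A reader might infer that providers have been clearing subjects for exercise without knowing of cardiac symptoms. The documents do not support that: the templates are unseen, and nothing is reported about what providers knew. A reader might also infer from the Exclusion Criteria that uncleared subjects must abstain. That text is discretionary. The firm condition is the one in Medical Clearance Process on returning the form.

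**Conclusion.** The point holds as a mismatch within the protocol. The letter sentence covers four of the five clearance categories and omits the one most relevant to physical activity. It also omits the hospital and emergency questions, so that 7 of 12 triggers are unnamed. Followed as written, it would give the provider less than the decision needs. Separately, encouragement not to engage is weaker than the section's own condition on the returned form.

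The size is small. The number affected is unknown and may be zero if the templates are complete, and at most 10 subjects remain who could benefit. The conclusion rests on the protocol's description of the letter and on enrollment being otherwise closed. It is a point of safety procedure and does not affect the outcomes or the analysis. It is worth acting on because a symptom left out could be cardiac and the correction costs very little.

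**What to change.** In Medical Clearance Process:

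1. State that the letter lists every screening item the subject answered positively, and BMI where it meets the threshold.
2. Check that the uploaded letter template and permission form do this, and that the release form the subject signs covers disclosure of all these answers.
3. Replace the encouragement not to engage with an instruction not to take part in uncleared components until the completed form is returned. This matches the condition already in that section. Keep the physician-investigator's option to halt participation altogether.

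The cost is two sentences and a template check in one modification, with edits to the template or release form only if they fall short. The answers are already collected at screening, so no new data or visit is needed. It should be in place before the last group starts in mid-August 2023.

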- 7 **Vulnerable Subjects.** There are no special classes of individuals who may be considered vulnerable subjects that are targeted for enrollment in this study. Specific modifications have been made to make this study culturally and linguistically appropriate for use with Deaf participants. The researchers who have direct contact with study subjects, including the researchers who obtain informed consent and deliver the health intervention modules, will be fluent in ASL. This research includes the guidance of Deaf community advisory boards, whose members are deaf adult ASL-users. No children will be included in the research. Prisoners or institutionalized individuals will not participate in this research.

III. METHODS AND PROCEDURES

Overall study design

The overall design of the DWW Implementation Study will have up to nine sites hosting DWW in three cities. NCDHR is working with each site to establish a timeline for beginning the program; as each new site is added, we will upload their Letter of Cooperation as a Modification to our application (we will upload each Letter of Cooperation as an amendment, once they are received). It is important to note that these sites are NOT engaged in the research, as per the federal definition.

The total length of the full study at each site is about 18 months for individual participants (baseline and two follow-up data collection points). Interventions will consist of 16-week group counseling Zoom sessions led virtually by trained, ASL-fluent Deaf counselors. Following the

16-week intervention, subjects will enter a 6-month “maintenance phase” with less intense interventions. This study is by definition a single-arm interventional clinical trial; we will register this study on clinicaltrials.gov as required, and will submit a modification to enter the NCT number prior to conducting the study.

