Study enrollment virtual visit and baseline data collection

If the subject is eligible as per the study screening interview, they will continue with the initial study enrollment visit via Zoom or videophone (1:1 with a research coordinator) to complete the following baseline activities:

- 1) Potential subjects will view the informed consent video in ASL which includes an overview of the DWW study. They will also have a one-on-one discussion with a member of the research team through Zoom or videophone to obtain informed consent if they are interested in participating. (see Consent Process section of Protocol)
- 2) Following the consent process, subjects will assigned a study ID number and will be asked to complete the one-on-one qualitative baseline health interview in ASL (included with this application).
- 3) The research coordinator will inform the subject that they then need to complete a baseline health survey on a REDCap website, which they will be instructed to do on their own time (see English version of surveys included with this application). They will be given their study ID number to enter into the REDCap survey to ensure their survey is completed. There are no other identifiers in the REDCap survey.
- 4) The research coordinator will work with the subject to fill out the Participant Contact Form also available in REDCap to be able to contact the participant for intervention scheduling and future follow up appointments (see PDF version of this form included with this application).

Modification July 13, 2023: As of this date, we have one implementation partner, the YMCA, who has not yet implemented an intervention group. The DWW intervention counselor for this group is now trained and ready to lead a group of participants starting in mid-August 2023. We will now recruit and enroll up to 10 participants for this virtual intervention group. Due to funding for this study ending in September 2024, we propose here to change the final data collection appointment for these final 10 participants only, so their final appointment will be 12 months

from enrollment instead of 18 months from enrollment. We will make this change to the Study Information Sheet (please see Consent section of protocol). All other study activities will be the same as what is already approved.

Post-intervention virtual data collection

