Subjects will have 6-month and 18-month follow-up appointments via Zoom or videophone, to assess change since baseline as well as post-intervention outcomes. The one-on-one qualitative health interview with a researcher and the REDCap health survey will be repeated at the 6-month and 18-month time points (see English version of surveys included with this application). These visits do NOT require in-person contact; they are all virtual.

Modification July 13, 2023: For the 10 participants in the YMCA-based virtual intervention group: Due to funding for this study ending in September 2024, we propose here to change the final data collection appointment for these final 10 participants only, so their final appointment will be 12 months from enrollment instead of 18 months from enrollment. Study coordinators will use the same 18-month data collection measures forms at the 12-month appointment with these 10 participants.

Health Survey in REDCap (see Table 1 below): Some data collection will be carried out in sign language along with English text version on a REDCap survey. We have developed a special external module in REDCap in collaboration with the REDCap creators at Vanderbilt University, which allows all of our survey questions to have ASL video in addition to English text, as well as unique features such as color changes and text size changes for use with Deaf-Blind respondents. At the beginning of the survey, the subject chooses a “sign model” to guide them through the survey, based on their preferred language and/or communication style (ASL or English-based sign language). The REDCap survey also has the ability to show instructions on how to use the survey. Once the survey begins, each survey item and response is shown in sign language video, followed by the English text of the question and response choices. The respondent enters or clicks on their response (and has the option to skip the item if they do not want to respond) using the mouse or touch screen technology depending on what device they use. Respondents can choose a different sign model at any point in the survey, and English captions can be turned on or off at any time.

[figure not shown]

Table 1. Data collection measures with DWW subjects

Measure/Description	Baseline	6 mo	18 mo	Mode of Administration
Demographics				
Deaf demographics				
Health history	X	X	X	Computer-based survey in ASL
Healthcare access				
Weight loss history				

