Primary Outcome #1: Site-level outcome: Implementation of the Deaf Weight Wise intervention at partner sites

Description: Number of partner sites implementing the DWW intervention

Time Frame: implementation of the DWW group intervention by the partner site after enrollment of at least 5 participants at that site

Primary Outcome #2: Site-level outcome: Percentage of Deaf Weight Wise intervention groups delivered as intended

Description: the study team will measure whether the intervention is delivered at each site as intended, as assessed by direct observations of the counselor/group and by bi-weekly counselor meetings

Time Frame: during each site's intervention and maintenance phases

We describe here **the individual-level analyses of subject data**.

At the completion of each of the three data collection periods, cleaned data will be summarized for frequencies of discrete variables and descriptive statistics of continuous variables, using SAS and other statistical packages. Continuous variables which show significant skewness and kurtosis will undergo log or square root transformation to approach a normal distribution. Tables will be constructed for baseline characteristics of the total study population and each site.

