The individual-level analyses will be carried out using paired t-tests to examine significance of differences in weight between baseline and the remaining data collection points. Other variables associated with individual outcomes of body weight will be identified using univariate analysis of correlation analysis or tests for multiple group comparison. Heterogeneity among sites can be explored by marginal analysis and model-based conditional analysis. Multiple regression analyses, including analysis of covariance (ANCOVA), will be based on generalized linear models (GLM), specifically for this project, including multiple linear regression models for continuous outcomes and logistic regression for dichotomous outcomes. Random effects can be incorporated in GLMs to account for correlation among repeated measures. Several least-squares and likelihood based methods, such as the Pearson's chi-squared test, Hosmer-Lemeshow test, and likelihood ratio test can be used to test the lack of fit or violations of assumptions of GLMs. In case of high-dimensional data in different scales, standardization will be applied before model fitting and variable selection. Variable selection approaches using AIC or BIC criteria will be used to select the significant predictors. Penalized-based variable selection procedures such as LASSO or SCAD may be used to overcome the drawbacks of ad-hoc methods of stepwise, best subset selection, etc. Missing (drop-out) data will be handled by appropriate statistical methods, which include maximum likelihood and/or direct maximum likelihood inverse probability weighting, and multiple imputations.

Secondary analyses will be carried out using paired t-tests to examine significance of differences in weight, Block dietary scores and IPAQ physical activity scores between baseline and the remaining data collection points for each group. Similarly, the costs of interventions will be analyzed. Finally, other variables associated with individual outcomes of change in body weight, Block score, and IPAQ score will be identified using univariate analysis as described previously. For age, gender, and all baseline variables associated with outcomes at the $P < .10$ level of significance, multivariate linear regression analyses will be performed to adjust for possible confounders.

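### Does moving the YMCA group's final visit to 12 months, on the 18-month forms, undermine the final-visit analyses?

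*Combined protocol and SAP*

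**What the plan says.** Section III (Post-intervention virtual data collection) sets follow-up at 6 and 18 months; the interview and survey "will be repeated at the 6-month and 18-month time points". Table 1 has columns for baseline, 6 and 18 months only, and the overall design text describes about 18 months per participant.

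The July 13, 2023 modification concerns the one partner that had not yet run a group: "We will now recruit and enroll up to 10 participants for this virtual intervention group". Funding ends in September 2024, so the last visit is moved, "so their final appointment will be 12 months from enrollment instead of 18 months from enrollment". On the instruments it says: "Study coordinators will use the same 18-month data collection measures forms at the 12-month appointment with these 10 participants". The same change is carried into the consent text and the payment text in section V, where the visit is again called a 12-month visit.

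The Data Analysis text has no matching entry. Summaries are produced "At the completion of each of the three data collection periods", and the secondary paired t-tests examine "differences in weight, Block dietary scores and IPAQ physical activity scores between baseline and the remaining data collection points for each group". On sites it says: "Heterogeneity among sites can be explored by marginal analysis and model-based conditional analysis". It gives no visit window, no elapsed-time term and no rule for the YMCA final records.

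**The concern.** With three periods, 18-month forms and no 12-month column, the obvious literal reading places 12- and 18-month measurements in the same third-period test. The two are not interchangeable. The 16-week programme plus 6 months of maintenance lasts about 9.7 months. If enrollment is close to group start, the final visit comes about 2.3 months after support ends for the YMCA and about 8.3 months after for everyone else. A pooled result would then describe neither time point exactly.

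There is also a site problem. If all 12-month records come from the YMCA and the YMCA has no 18-month records, a YMCA difference at the final visit cannot be told apart from six months less follow-up. Site heterogeneity and the Aim 4 associations have no stated time point, so the final visit is not ruled out for them.

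**Working it through.** **Which outcomes use the final visit.** Primary outcomes 1 and 2 are site-level implementation measures. Secondary outcomes 1 to 3 are changes from baseline to 6 months. None uses the final visit. What remains is the general text on paired tests and models, which attaches to no named outcome.

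**Inputs.** From the documents: 108 participants (9 sites × 10 in groups = 90; 9 × 2 one-on-one = 18; 90 + 18 = 108) and up to 10 at the YMCA. Assumed, because the documents give no figure: D, the mean weight change between months 12 and 18, 0.5–2 kg in either direction; SD of change 6 kg (4–8 kg also tried); lower totals of 60 and 40, since section V reports low enrollment in Buffalo and Syracuse in November 2022 without counts.

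**Shift from pooling** = share × D; SE = SD/√N.

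| N | Share | Shift (kg) | SE (SD 6) | Shift/SE |
|---|---|---|---|---|
| 108 | 10/108 = 9.3% | 0.05–0.19 | 0.577 | 0.08–0.32 |
| 60 | 10/60 = 16.7% | 0.08–0.33 | 0.775 | 0.11–0.43 |
| 40 | 10/40 = 25.0% | 0.13–0.50 | 0.949 | 0.13–0.53 |

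Coverage of a 95% interval for the 18-month mean is Φ(1.96 − b) − Φ(−1.96 − b), with b = shift/SE. This gives 94.9–93.8% at N = 108 and 94.8–91.8% at N = 40. At N = 108, an SD of 4 kg gives shifts of 0.12–0.48 SE and an SD of 8 kg gives 0.06–0.24 SE. If all 108 were seen, mean follow-up would be (98 × 18 + 10 × 12)/108 = 17.4 months.

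**Would leaving the records out do better?** As an estimate of the 18-month mean, pooling has mean squared error SD²/N + (share × D)²; exclusion has SD²/(N − 10). At SD 6 kg and D = 2 kg, the top of the range:

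- N = 108: 36/108 + 0.185² = 0.368 against 36/98 = 0.367.
- N = 60: 36/60 + 0.333² = 0.711 against 36/50 = 0.720.
- N = 40: 36/40 + 0.500² = 1.15 against 36/30 = 1.20.

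Setting the two equal gives a break-even of D = SD × √(1/10 + 1/(N − 10)): 1.99, 2.08 and 2.19 kg for the three totals at SD 6, and 1.33, 1.39 and 1.46 kg at SD 4. Below the break-even, pooling has the smaller error. Exclusion widens the interval by √(108/98) = 1.05, √(60/50) = 1.10 or √(40/30) = 1.15.

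**Site against follow-up length.** At the final visit alone, nine site indicators plus a 12-month indicator make 10 columns of rank 9, so the two effects cannot be separated. Over all visits, nine site indicators plus 6-, 12- and 18-month indicators make 12 columns of rank 12: the YMCA's baseline and 6-month data fix its site effect, provided sites share a common time course. The plan allows random effects for repeated measures, so such a model is within its terms. A final-visit contrast of the YMCA with the rest has SE 6 × √(1/10 + 1/98) = 1.99 kg, so a D of 0.5–2 kg shifts it by 0.25–1.0 SE. With at most 10 participants at one site, it is weak in any case.

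**The case for a change.** The best argument for acting is that a rule would cost a sentence and a table entry and could be set before any of these visits took place. The final visit is also the only one after support has ended, since the 6-month visit falls inside maintenance. Mixing 2.3 and 8.3 months off support blurs the one measurement of persistence. At an assumed total of 40, coverage could fall to 91.8%, and at SD 4 kg exclusion is better once D exceeds about 1.3–1.5 kg.

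These points stand as far as they go. It is true that the plan does not say how the records are labelled or analysed, and that a final-visit YMCA contrast would mix site with time. But after the modification 12 months is itself a data collection point, so the paired-test wording can equally be read as testing it separately. Using the same forms keeps the measures comparable and does not say that the visit is labelled 18 months. Baseline tables are planned by site, and the payment text ties the 12-month schedule to YMCA enrollment in July–August 2023, so the records can be found whatever form they are on.

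The overlap of site and follow-up length is also not proved to be complete. The modification says only that no YMCA group had run, while section III allows up to two one-on-one participants per site, who could have enrolled earlier on the 18-month schedule.

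**Conclusion.** No change is needed. The missing rule is a detail that an analyst fills in the ordinary way, by labelling the records by time since enrollment and saying in the report whether they are shown apart or pooled. The shorter follow-up is itself a fair trade-off: 18 months from a July–August 2023 enrollment falls in January–February 2025, after funding ends.

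No primary or named secondary outcome is touched. At the planned 108, pooling shifts a final-visit mean weight change by at most about 0.19 kg, or 0.32 SE at SD 6 kg (0.48 SE at SD 4 kg), and exclusion is no clear improvement. Separate analysis gives a cleaner 18-month estimand; pooling keeps the only mainstream community partner in the comparison. Either is defensible.

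This rests on the assumed D of 0.5–2 kg and SD of 4–8 kg, which the documents do not supply. The effect is larger if totals fall well short of 108. A YMCA difference seen at the final visit alone should not be read as a site effect; the 6-month visit, common to all sites, is the sounder basis for that comparison.
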